RCT. The final phase of the proposed project will implement an RCT to examine whether the program is feasible and associated with improvements in the treatment targets (see Measures and Figure 1). Thirty-six siblings will be recruited and randomly assigned to participate in Siblings FORWARD (N=18) or receive written materials about future planning (N=18). Siblings assigned to Siblings FORWARD will complete Time 1 (pre-program) measures, participate in the 6-session intervention over 4 months, complete Time 2 measures immediately after program completion, and complete Time 3 measures 3 months later. Those assigned to the control condition will complete Time 1 measures at the time of enrollment, Time 2 measures 4 months after enrollment, and Time 3 measures 7 months after enrollment. With the exception of the clinician rating of the sibling's ASD symptoms (see Measures), all data will be collected by the Boston University study team via home visits in order to separate data collection from the Arc providers. Adults with ADS and their families will determine whether the adult with ASD can complete the questionnaires (see Methods). When possible, the adult with ASD will complete the measures independently in the presence of a Boston University research team member. These measures can also be completed with the support of a research team member, sibling, parent, or service provider. Given possible geographic separation, sibling data will be collected via mailed questionnaire packets. We will track this data collection method to inform future data collection logistics.

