**Table 3: Program Description**

Target	Description
Session 1: Assessment & Motivation (Sibling) – 75 minutes	The initial session will assess the extent to which future plans are in place, the extent to which the sibling is informed about future plans, siblings' perceptions of their own and their families' motivation and readiness to engage in the process, family values regarding family roles and care preferences, and initial goals for sibling involvement in family future planning for the adult with ASD. This session will include a motivational interviewing component to increase siblings' engagement with future planning. Finally, the sibling will draft a first version of their plan of action, including high-level goals. Between-session tasks: (1) learn about the family's existing future plans (if any) and (2) refine their goals for program participation and role in the life of their brother/sister with ASD.
Session 2: Family Communication (Sibling) – 60 minutes	Siblings will be taught to use effective communication skills with their family members (e.g., parents and the individual with ASD). The sibling will be given instruction in basic communication skills (e.g., using "I" statements, reading others' body language, maintaining a collaborative tone, etc). Then, he/she will practice these skills in session by role-playing how they might talk to family members about their initial plan of action that was outlined in Session 1. The sibling will set specific goals regarding communicating with family members (parents, brother/sister with ASD, other siblings, etc.) about specific topics identified in session (e.g., financial planning). Between-session assignment: work toward meeting the family communication goals outlined in session.

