#### Proximal Outcomes: Sibling Behavior & Adults with ASD (Timing indicated below)

1. **Sibling Plan of Action (T2)**. Siblings will submit a written plan of action at the final session; control participants will complete this plan at Time 2. We will use a template on which siblings will detail their short- and long-term goals with respect to family future planning and concrete next steps. Researchers will rate each plan according to the following criteria: (1) inclusion of short- and long-term goals and next steps, (2) appropriate scope of next steps, (3) alignment with the needs and/or preferences of the adult with ASD, (4) accuracy (e.g., are they identifying the right resources to meet the identified goal?), and (5) sufficient detail (e.g., including the names and phone numbers of actual resources vs. making vague plans). At the 3-month follow up time point, we will assess whether or not the sibling attempted or achieved their primary short-term goal, the steps they took to achieve their goal, and concrete outcomes of the sibling's engagement in family future planning (e.g., family made an appointment with a special needs lawyer).
2. **Adult with ASD: Quality of Life (T1 & T3). Proxy report**: Siblings will rate their brother/sister's quality of life using the Life Experiences Checklist. This has been used as a proxy-report measure by family members and support staff to rate the QOL of adult with ASD. Five sections cover the individual's home environment, leisure activities, relationships, freedom, and opportunities. **Self-report**: Adults with ASD will complete the WHOQOL-BREF, a shorter version of World Health Organization Quality of Life assessment, the WHOQOL-100, which includes 26 items rated on a 5-point scale addressing physical and psychological health, social relationships, and environment. This measure has been used with adults with ASD, including [name] collaborative study with [name]. We will modify administration as described by Hong and colleagues to ensure greater accessibility across the autism spectrum.

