Acceptability (open trial and RCT): Qualitative data about perceptions of program usefulness and value collected during exit interviews with providers and participants will be evaluated using the qualitative methods outlined for Aim 1. Participant understanding of measures and procedures (open trial): Missing data and inconsistent response patterns on measures completed by siblings will be recorded. Data collection time will be calculated descriptively (mean, standard deviation, and range); participant burden associated with completing study measures will be captured qualitatively and summarized using content analysis. Enrollment and retention (RCT): Enrollment will be evaluated by calculating the number of eligible participants who chose to enroll in the trial. Descriptive statistics show the average number of sessions completed by participants and retention and follow-up rates. To assess selective attrition, we will evaluate the demographic and clinical characteristics of participants who completed the program versus those who did not using t-tests and chi squares. Adherence (RCT): Providers' fidelity to the manual will be assessed by evaluating video recordings of sessions against checklists of required components and calculating the percentage of required components that were present in each session; 20% of sessions will be coded for fidelity. Appropriateness of outcome measures (RCT): Psychometric properties of measures (alpha coefficients, means, SDs) and descriptive statistics of change scores from pre- to post-program time points (including confidence intervals) will be calculated.

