*Aim 3: To assess the outcomes of participation in the Siblings FORWARD program.* We will examine whether the program shows promise of being successful with the intended population by conducting two-way repeated measures ANOVAs examining main effects of intervention condition (Siblings FORWARD vs. control) and repeated for assessment (pre- post- and 3-month follow up) on measures for program targets (sibling problem solving skills, family communication, future planning self-efficacy, barriers to future planning, and knowledge of services and family future plans) and proximal outcomes (sibling plan of action and adult with ASD quality of life, perceptions of unmet needs, and family relationships). Post-hoc tests will be used in multiple comparisons between groups and within each group. Effect sizes (Cohen's d) will be calculated using the mean difference of the changes recorded from pre- to post-program. We will also analyze percent change and reliable change. If data are missing, analyses will be performed using the 'last observation carried forward' method for intention-to-treat analysis. We will examine descriptive statistics (mean, SD, confidence intervals) at the participant level for patterns and direction of change on outcome measures. We will conduct intent-to-treat analyses if there is program attrition. Finally, we will examine benefit of the program to control participants who elect to participate in the Siblings FORWARD program using one-way ANOVAs (pre to post-program) on treatment targets and proximal outcomes.

We will conduct a preliminary investigation of potential moderators of program effectiveness, including characteristics of the sibling (BAP), family (income, race/ethnicity, English as the primary language, number of family members with ASD), and adult with ASD (severity of ASD symptoms, problem behaviors, functional independence). We will calculate correlations between these variables and change scores in primary outcome variables, and independent samples t-tests between these variables and program completion status.

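### Program siblings who stop early have no stated Time 2 or Time 3 date and no route for collecting their plan of action, and LOCF cannot supply a missing plan rating

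*Combined protocol and SAP*

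**What the plan says.** The RCT paragraph under Procedures sets two kinds of schedule. Program siblings do a six-session program planned to take 4 months, then "complete Time 2 measures immediately after program completion, and complete Time 3 measures 3 months later". For the other arm: "Those assigned to the control condition will complete Time 1 measures at the time of enrollment, Time 2 measures 4 months after enrollment", with Time 3 at 7 months.

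The plan of action follows the same split. Under Proximal Outcomes: "Siblings will submit a written plan of action at the final session; control participants will complete this plan at Time 2". It is labelled a Time 2 measure and is rated by researchers on five criteria. At the 3-month follow-up the sibling is asked about progress on the main short-term goal.

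Data Analysis, Aim 2, expects some siblings not to finish. It compares "participants who completed the program versus those who did not" on demographic and clinical characteristics, and separately reports "retention and follow-up rates". Aim 3 promises intent-to-treat analysis if there is attrition, and gives one missing-data rule: "If data are missing, analyses will be performed using the 'last observation carried forward' method for intention-to-treat analysis".

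**The concern.** A program sibling who leaves before Session 6 never completes the program and never attends the final session, so neither event that triggers assessment occurs. Controls have calendar dates and meet no such obstacle. The protocol therefore anticipates a group of randomised siblings for whom it sets no assessment date and no way of obtaining the plan.

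The Approach overview gives the creation of a plan of action as one of the things the RCT is meant to examine. If early leavers are not asked for a plan, that comparison sets self-selected program finishers against all assessed controls and is no longer protected by randomisation. The Aim 2 comparison of completers with non-completers cannot reveal the problem, because it does not cover outcomes that were never collected.

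**Working it through.** **Which outcomes LOCF can fill for an unassessed early leaver**

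- Program targets (Times 1, 2 and 3): a missing Time 2 takes the Time 1 value, so change is zero. A missing Time 3 takes the Time 2 value, or Time 1 if Time 2 is also missing.
- Quality of life (Times 1 and 3): a missing Time 3 takes the Time 1 value.
- Plan of action (Time 2 only): there is nothing to carry forward. Table 3 says of Session 1 "Finally, the sibling will draft a first version of their plan of action, including high-level goals". Sessions 4 and 5 and the shared-desktop documents can take that draft further. None of these working versions is a rated outcome, and none has a control counterpart.
- Goal attainment at Time 3: it presupposes a plan and has no earlier value, so it has the same gap.
- Unmet needs and family relationships: no assessment times are given, so a Time 1 value to carry forward is not established.

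**Plan of action: size of the distortion**

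The documents give 18 siblings per arm but no dropout rate and no expected share of adequate plans, so there is no figure of the plan's own to reproduce. Assume a share pF = 0.80 of finishers and pN = 0.30 to 0.80 of non-completers (if asked) would produce an adequate plan, with a share d of the program arm missing.

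True program-arm rate = (1 − d)·pF + d·pN.

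Finishers-only analysis reports pF, so it overstates by d·(pF − pN). Scoring missing plans as no plan reports (1 − d)·pF, so it understates by d·pN.

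| d (of 18) | Finishers-only overstates | No-plan scoring understates |
|---|---|---|
| 10% (about 2) | 0.10 × (0 to 0.50) = 0 to 5 points | 0.10 × (0.30 to 0.80) = 3 to 8 points |
| 20% (about 4) | 0 to 10 points | 6 to 16 points |
| 30% (about 5) | 0 to 15 points | 9 to 24 points |

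The two treatments err in opposite directions, and the protocol does not choose between them.

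**Precision**

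Assuming two-sided 0.05 and 80% power, the minimum detectable standardised difference is (1.960 + 0.842)·√(1/18 + 1/n). This gives 0.93 at n = 18, and 0.96, 1.00 and 1.04 at n = 16, 14 and 12. The loss is modest; selection matters more.

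**Questionnaires**

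LOCF sets the change of missing siblings to zero. The bias in the Time 2 minus Time 1 arm difference is therefore −dP·MP + dC·MC, where d is the share missing, M is the true mean change of those missing, and P and C are program and control. Assume control dropouts change by +0.3 SD and program dropouts by anything from +1.1 to −0.3 SD.

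- 30% vs 5% missing, none followed: −0.30 × 1.1 + 0.05 × 0.3 = −0.315, to +0.30 × 0.3 + 0.015 = +0.105 SD.
- 10% vs 5% missing: −0.11 + 0.015 = −0.095, to +0.03 + 0.015 = +0.045 SD.
- 30% vs 5% with 80% of those followed, so 6% vs 1% missing: −0.066 + 0.003 = −0.063, to +0.018 + 0.003 = +0.021 SD.

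A simulation compared LOCF with a random-intercept mixed model on all observed data (18 per arm, within-person correlation 0.6, controls +0.3 SD, program finishers +1.1 SD, 2,000 runs per scenario). At 30% vs 5% with none followed, mixed-model bias ran from 0.00 to +0.40 SD. With 80% followed it ran from 0.00 to +0.06 SD, and root mean squared error was 0.30–0.33 against 0.30–0.32 for LOCF. The improvement comes from following people up, not from changing the method.

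**The case against.** The strongest defence is that non-completers probably will be followed and only the date was left out. A 4-month program followed by a 3-month interval puts the program arm nominally at months 4 and 7, which matches controls. The plan of action carries a Time 2 label for both arms. The university team, not the Arc providers, collects nearly all the data, and sibling packets are mailed, so leaving the program need not end assessment. Follow-up rates are reported separately from sessions completed, and intent-to-treat is promised.

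All of that stands, and it rules out one tempting inference: that the protocol intends to leave non-completers unassessed. It does not say so. But intent-to-treat governs how data are analysed, not when they are collected, and a nominal month 4 is not a rule for someone whose Time 2 is defined by an event that never happens.

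Three further inferences also go too far. A reader might suppose that an early leaver can hold only the Session 1 draft; later sessions revise it. A reader might take the plan as the only outcome LOCF cannot fill; goal attainment shares the gap, and two measures have no stated times. A reader might assume that LOCF must work against the program, or that a mixed model would cure the problem. The LOCF bias can take either sign, and the mixed model can overstate the effect when dropouts do worse.

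**Conclusion.** The gap is real: no assessment date and no plan-collection route exist for program siblings who stop early, and the stated missing-data rule cannot produce a plan rating for them. The harm is conditional on those siblings actually going unassessed and on how many there are. Under the assumed adequacy rates it runs from nothing to 5 percentage points on the plan of action at 10% missing, and up to 15 points at 30%. Questionnaire bias is under 0.10 SD at 10% vs 5% missing, but can reach about 0.3 SD at 30% vs 5% with no follow-up. Every dropout rate, adequacy rate and change used here is an assumption. For a pilot this should be corrected: it touches a named purpose of the RCT, and the correction is cheap.

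**What to change.** **Procedures (RCT) and Proximal Outcomes.** State that every randomised sibling is asked for Time 2, the plan-of-action template and Time 3 regardless of sessions completed. Program siblings who stop early or have not finished on schedule are assessed at the control arm's times, 4 and 7 months after enrollment, within a stated window. Analyse by assigned arm.

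**Data Analysis, Aim 3.** State that LOCF does not apply to the plan of action, report missing plans by arm, and add a sensitivity analysis scoring missing plans as no plan. A mixed model on all observed data alongside LOCF is optional.

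**Cost.** A few sentences of text. The template can go in the mailed packet. The follow-up interview items on the family's plans and the measures completed by the adult with ASD need a few extra contacts with non-completers. Some slow finishers will be assessed before Session 6, and their Time 3 will fall less than 3 months after it. Using the control arm's existing times adds nothing to the nominal 7-month schedule, so Table 4 is no tighter than it already is.

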### **Sample & Recruitment**

Community Advisory Board. Future planning for adults with ASD is complex due to the multiple systems of care, frequent perceptions of unmet needs, legal and ethical considerations, and emotional aspects. This complexity increases the challenges of creating a program such as Siblings FORWARD and will require early and frequent involvement of stakeholders with experiences relevant to adults with ASD. Thus, the first step of the proposed research will be to engage members of the community advisory board (CAB). We have assembled a team with personal and/or professional expertise related to adult ASD (Table 2). These individuals have already agreed to serve on the CAB (see Support Letters); therefore, meetings will commence immediately if the project is funded. The CAB will meet quarterly during the project in order to (1) provide feedback on initial drafts of the program content and implementation plan, including identifying unanticipated barriers, (2) strengthen our ties with the community in which the intervention will be implemented currently and in the future, and (3) ensure community acceptability to support future implementation and dissemination. To ensure the quality of feedback and strength of relationships, CAB meetings will be held in-person at a convenient time and location.

Service Providers. Five focus groups will be conducted (N=6-8 members in each group) to obtain feedback on the content and format of the program, including three focus groups with adult siblings and two with providers experienced in serving adults with ASD and their families. Service providers will be recruited primarily through local Arc organizations (e.g., family support staff). There are 10 Arc chapters located within a 30-mile radius of Boston; we will also conduct service provider focus groups at the Arc’s national convention. This is adequate to ensure a sample size of 12-16 providers for focus groups.

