Siblings and Adults with ASD. *Siblings* will be enrolled in three focus groups (N=18-24), the open trial (N=5), and the RCT (N=36). For focus groups, siblings who live in the greater Boston area will be enrolled. For the open trial and RCT, siblings will be enrolled regardless of their geographic location; this is possible due to the telehealth delivery format. Sibling inclusion criteria include (1) one or more adult brother(s) or sister(s) with ASD who are either biologically related and/or were raised in the same family of origin (e.g., adopted, step, or foster siblings), (2) age 18+, and (3) English fluency. Siblings will be excluded if they have a disability that would interfere with their ability to engage meaningfully in future planning for the adult with ASD. *Adults with ASD* (N=8-10) will participate in individual interviews during the first stage of the project and will complete self-report measures during the open trial and RCT if capable (with support if needed). Inclusion criteria for the adults with ASD include (1) an ASD diagnosis, (2) an adult brother/sister (i.e., a sibling), (3) age 21+, and (4)

Table 2: Community Advisory Board	
Name	Expertise / Role
[name]	Adult with ASD
[name]	Adult sibling; Co-founder of Sibling Leadership Network
[name]	Parent of youth with ASD & lawyer
[name]	Arc of Massachusetts
[name]	Director of Adult Services, AANE, & parent of youth with ASD

English fluency if verbal. For the focus groups, adults with ASD will be excluded if their abilities would preclude participation in an interview about future planning (e.g., due to significant cognitive or language challenges).

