3. **Adult with ASD: Unmet Needs**. Adults with ASD will report on their perceptions of unmet needs using items that Nicolaidis and colleagues adapted for adults with ASD using items from the 2002/ 2003 Joint US Canada Survey and 2007 National Health Interview Survey Questionnaire—Adult Access to Health Care and Utilization. They will report on unmet needs in medical care, mental healthcare or counseling, preventive services, emergency department visits, outpatient visits, and hospitalizations. In collaboration with the CAB, we will add items probing unmet needs in residential and occupational domains.
4. **Adult with ASD: Perceptions of Family Relationships**: Adults with ASD will complete the 11-item Family subscale of the Social and Emotional Loneliness Scale for Adults (e.g., "No one in my family cares about me," "I wish my family were more concerned about my welfare"). This scale has adequate reliability and validity and has been used in adults with ASD.

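### The adult's self-reports may be completed with help from the randomised sibling or from a provider who may deliver the program, and the helper is neither restricted nor recorded

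*Combined protocol and SAP*

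**What the plan says.** The RCT paragraph of the Procedures states that, apart from the clinician rating of the sibling, "all data will be collected by the Boston University study team via home visits in order to separate data collection from the Arc providers". For the adult with ASD the preferred mode is independent completion: "When possible, the adult with ASD will complete the measures independently in the presence of a Boston University research team member". The next sentence widens this: "These measures can also be completed with the support of a research team member, sibling, parent, or service provider". Sample & Recruitment likewise allows support where needed and does not say from whom.

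Three outcomes are self-reported by the adult (Measures, Proximal Outcomes): the WHOQOL-BREF, unmet needs, and family relationships. On the last, "Adults with ASD will complete the 11-item Family subscale of the Social and Emotional Loneliness Scale for Adults"; its sample items ask whether the family cares about the respondent. The sibling separately gives a proxy rating of the adult's quality of life. Data Analysis, Aim 3, compares all of these outcomes between arms.

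**The concern.** Two kinds of permitted helper have an interest in the answers.

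- **A provider.** If this is the Arc staff member who ran the sessions, the person delivering the program helps to produce its outcome data. The separation aim exists to prevent that.
- **The randomised sibling.** The sibling knows the arm and is one of the people the family items are about. A sibling who helps with the self-report and also completes the proxy quality-of-life form makes two nominally separate sources dependent on each other.

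The self-reports are the only outcomes that come from the adults themselves. At stake are the interpretability of their between-arm comparison and the pilot's ability to judge whether these measures suit a larger trial. A change of helper between assessments would also add noise to change scores.

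**Working it through.** **1. Does provider help fit the separation aim?** The RCT paragraph names one exception to collection by the university team: the clinician rating of the sibling. Provider support for the adult's questionnaires is not listed as another.

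**2. Who is a service provider?**
- Sample & Recruitment (on focus groups): drawn mainly from local Arc organizations.
- Procedures, Open Trial: service providers are trained to deliver the program.
- Siblings FORWARD Program Description: sessions are guided by Arc family support staff.

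The term therefore includes the people who deliver the program. The RCT paragraph does not say that the helper would be one of them, and does not exclude them.

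**3. Is the helper controlled or recorded?** There is no order of preference among helpers, no limit on what support may consist of, no record of who helped, and no analysis by mode of completion. The sentence about tracking the data collection method follows the one on mailed sibling packets and most naturally refers to those.

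**4. Could the effect differ by arm?** Program-arm siblings have six provider-led sessions, and Session 5 brings provider, sibling and adult together where possible. Under Control Condition, control siblings are offered the program only after all outcome data are in. At follow-up a program-arm helper may therefore have a stake that a control-arm helper lacks. This is a mechanism, not evidence of a shift.

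**5. Size (illustration only).** The plan gives no figure to reproduce: no share needing help, SD, alpha or power. Let f be the share of program-arm adults helped by the sibling or a provider (not by anyone at all), and b the resulting shift in SD units relative to control. Both are assumptions. With 18 per arm and no true effect:

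- spurious difference d = f × b
- SE = √(2/18) = 0.333
- false-positive probability = 1 − Φ(1.96 − d/SE) + Φ(−1.96 − d/SE), assuming two-sided 0.05

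| f | b | d | d/SE | False-positive probability |
|---|---|---|---|---|
| 0.25 | 0.2 | 0.05 | 0.15 | 5.3% |
| 0.25 | 0.5 | 0.125 | 0.375 | 6.6% |
| 0.50 | 0.5 | 0.25 | 0.75 | 11.7% |
| 0.75 | 0.5 | 0.375 | 1.125 | 20.3% |
| 1.00 | 0.8 | 0.80 | 2.40 | 67% |

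If help shifts answers equally in both arms, b = 0 and so d = 0. The calculation is a simple two-group comparison, not the planned repeated-measures ANOVA. It also takes all 18 adults per arm as responding. Adults respond only if capable, so the real SE would be larger and d/SE smaller.

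**The case against.** The strongest reply is that the aim concerns who collects the data, and the university team still does so. Independent completion is the default, and support is a fallback. The helper list says service provider rather than Arc provider, and an adult may have other providers, such as personal care staff. The delivering provider works by video from an office, while collection is by home visit. Siblings may live far away, which is why their own forms are mailed. Much of this stands: it makes provider help a tension to resolve rather than a reversal of the design, and it may make sibling help uncommon. It does not remove the point, because the text permits both and would leave no record of either.

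A reader might infer that sibling help also contradicts the separation aim. It does not, since that aim names only Arc providers. A reader might also infer that bias is established and confined to the program arm. The documents do not show this: control siblings also know their arm and may also help, and an equal shift cancels.

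Two further objections are fair. Parents are also covered by the family items and may know the arm, and the plan does not say that research staff are masked. No choice of helper is free of this problem. Improvement in the adult outcomes is also described in places as longer-term, which limits the consequence for a pilot, although Aim 3 does analyse them as proximal outcomes.

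**Conclusion.** The concern holds as a modest and inexpensive improvement. The plan permits arm-aware, interested helpers on three outcomes that it compares between arms. Provider help is in tension with the plan's own separation aim; sibling help is a separate unblinded-helper problem. Either could bias the comparison, potentially more in the program arm.

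The direction and size are unknown. The range of 0.05 to 0.80 SD rests wholly on assumed f and b, and no single value in it should be read as an estimate. An argument about change from Time 1 to Time 3 is documented only for quality of life, because the Measures section gives no timing for unmet needs or family relationships.

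**What to change.** Amend the RCT paragraph of the Procedures as follows:

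- Make the university research team member at the visit the default source of support.
- Do not use the randomised sibling or the provider delivering the program as helper.
- Allow a parent or other familiar communicator not involved in the program when the adult could not otherwise respond.
- Record the helper and the mode of completion at each assessment, and keep the same helper across assessments where feasible.
- In Data Analysis, Aim 3, add a sensitivity analysis of the adult self-reports by mode of completion.

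The cost is protocol wording, a short addition to the form and one descriptive analysis. A team member is already expected at the visit, so extra staffing should not be needed. The downside is that some adults with greater support needs may give fewer or less complete answers. Under the current plan those gaps would be filled by last observation carried forward, so the extent of missing answers should be reported alongside the results.
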